6.6 Measures to Minimize Bias: Randomization and Blinding

6.6.1 Subject Identification

Subject identification numbers will be assigned sequentially to the subjects who have consented to participate in the study, according to the range of subject identification numbers allocated to the study center.

6.6.2 Treatment Allocation to the Subject

Treatment numbers will be allocated by dose.

The enrollment will be performed to ensure equal distribution of the population within the age strata (subjects 18-45 years of age versus subjects 50-70 years of age).

Allocation of the subject to a study group at the study center will be performed using SBIR. As the study will enroll 2 age groups sequentially through 4 steps (Step 1: 18-45 years of age and Steps 2, 3, and 4: 50-70 years of age), the steps will be considered as stratification factors with a specific size and group ratio at each step (Step 1: 20 subjects with ratio 1:1 between CDIFF Ag

and placebo alone; Step 2: 20 subjects with ratio 1:1 between CDIFF Ag and placebo alone, Step 3: 30 subjects with ratio 1:1:1 between CDIFF Ag, CDIFF Ag + AS01_B and placebo; Step 4: 70 subjects with ratio 5:7:2 between CDIFF Ag, CDIFF Ag + AS01_B and placebo). Within the 18-45 years age group, the randomization algorithm will use a minimization procedure accounting for gender (female, male), while within the 50-70 years age group, the randomization algorithm will use a minimization procedure accounting for age (50-59 years of age, 60-70 years of age) and gender (female, male). Minimization factors will have equal weight in the minimization algorithm. A minimum of 20% of each minimization factor category will be required to allow enrolling all categories within each minimization factor (refer to Section 8.11 for study procedures to be considered during special circumstances).

After obtaining the signed or witnessed/thumb printed and dated informed consent form (ICF) from the subject and having checked the eligibility of the subject, the study staff in charge of the vaccine administration will access SBIR. Upon providing the age (subjects 18-45 years of age versus subjects 50-70 years of age), the gender, and the subject identification number, the randomization system will determine the study group and will provide the treatment number to be used for the first dose.

The number of each administered treatment must be recorded in the eCRF on the Vaccine Administration screen.

When SBIR is not available, please refer to the SBIR user guide or the SPM for specific instructions.

6.6.2.1 Treatment Number Allocation for Subsequent Doses

For each dose subsequent to the first dose, the study staff in charge of the vaccine administration will access SBIR, provide the subject identification number, and the system will provide a treatment number consistent with the allocated study group.

6.6.3 Blinding

Data will be collected in an observer-blind manner. By observer-blind, it is meant that during the course of the study, the vaccine recipient and those responsible for the evaluation of any study endpoint (eg, safety and reactogenicity) will all be unaware of which vaccine was administered. To do so, vaccine preparation and administration will be done by authorized medical personnel who will not participate in any of the study clinical evaluations. The Investigator and the subjects will not have access to the treatment allocation up to Day 390.

The statistical analyses will be performed in 3 steps. Refer to Section 9.8 for controlled unblinding for the first and second interim analysis.

The data for third dose will be collected in a partial blind manner.

After Day 390, only the subjects will remain fully blinded. Those responsible for the evaluation of any study endpoint (eg, safety and reactogenicity) will be partially blinded, as no placebo subjects will be included for Dose 3.

The laboratory in charge of the laboratory testing will be blinded to the treatment, and codes will be used to link the subject and study (without any link to the treatment attributed to the subject) to each sample.

6.6.3.1 *Emergency Unblinding*

Unblinding of a subject's individual treatment code should occur only in the case of a medical emergency when knowledge of the treatment is essential for the clinical management or welfare of the subject.

The emergency unblinding process consists of the automated internet-based system (SBIR) that allows the Investigator to have unrestricted, immediate and direct access to the subject's individual study treatment.

As back-up process, the Investigator has the option of contacting a GSK Helpdesk (refer to [Table 16](#)) if he/she needs support to perform the unblinding (ie, he/she cannot access SBIR).

Non-investigator physician (eg, physician from emergency room) or subject/care giver/family member can also request emergency unblinding either via the Investigator (preferred option) or via the GSK Helpdesk (back-up process). Contact details of Investigator and GSK Helpdesk are reported in the subject card.

Table 16 Contact Information for Emergency Unblinding

GSK Helpdesk
24-hour and 7-day availability
The Helpdesk is available by phone, fax and email
Toll-free number: [name]
[contact]
[contact]
email: [contact]

A subject may continue in the study if that subject's treatment assignment is unblinded.

GSK Vaccines Clinical Safety and Pharmacovigilance staff may unblind the treatment assignment for any subject in case of Suspected Unexpected Serious Adverse Reaction (SUSAR) as well as in case of fatal or life-threatening cases. If the SAE requires that an expedited regulatory report be sent to 1 or more regulatory agencies, a copy of the report, identifying the subject's treatment assignment, may be sent to Investigators in accordance with local regulations and/or GSK policy.

6.7 Study Treatment Compliance

The prescribed dosage, timing, and mode of administration may not be changed.

All dose administrations will be performed in the study center under the supervision of appropriately trained staff.

6.7.1 Treatment Strategy

The study center staff is responsible for the ongoing safety and wellbeing of the subjects while they are in the study center. There is a paging system to alert the clinical staff to any area in the center where a subject may need medical attention. There is medical advice available by phone 24 hours a day. In addition, if necessary, the clinical staff can contact further on-call physicians or public emergency services in the event of a serious medical event.

6.7.2 Warnings and Precautions

As this is the first administration of study treatment to humans, all effects cannot be reliably predicted. The preclinical data suggest an acceptable safety margin. Facilities and staff for resuscitation and the treatment of other medical emergencies will be provided.

6.8 Concomitant Therapy

6.8.1 Recording of Concomitant Medications/Products and Concomitant Vaccinations

At each study visit, the Investigator or delegate should question the subject about any medications/products taken and vaccinations received by the subject.

The following concomitant medication(s)/product(s)/vaccine(s) must be recorded in the eCRF:

- All concomitant medications/products, except vitamins and dietary supplements, administered between Day 1 and Day 61.
- All concomitant medications/products, except vitamins and dietary supplements, administered between Day 491 and Day 521.
- Any concomitant vaccination administered in the period starting 6 weeks before the first dose of study treatment and ending at the last study visit (Day -42 to Day 390 for subjects receiving 2 doses/Day 670 for subjects receiving 3 doses).
- Prophylactic medication (ie, medication administered in the absence of ANY symptom and in anticipation of a reaction to the vaccination).

An antipyretic is considered to be prophylactic when it is given in the absence of fever and any other symptom, to prevent fever from occurring (fever is defined as temperature $\geq 38.0^{\circ}\text{C}/100.4^{\circ}\text{F}$ regardless the location of measurement). The preferred location for measuring temperature in this study will be the oral cavity.

- Any concomitant medications/products/vaccines leading to the withdrawal or non-eligibility of the subject from the study (refer to Section 6.8.2).
- Any concomitant medications/products/vaccines relevant to an SAE/pIMD to be reported as per protocol or administered during the study period for the treatment of an SAE/pIMD. In addition, concomitant medications relevant to SAEs and pIMDs need to be recorded on the expedited AE report.

6.8.2 Concomitant Medications/Products/Vaccines That may Lead to the Elimination of a Subject From Per-protocol Analyses

The use of the following concomitant medications/products/vaccines will not require withdrawal of the subject from the study but may determine a subject's evaluability in the per-protocol analysis. See Section 9.3 for populations to be analyzed.

- Any investigational or nonregistered product (drug or vaccine) other than the study vaccine(s) used during the study period.
- Immunosuppressants or other immune-modifying drugs administered chronically (ie, more than 14 consecutive days in total) during the study period (until Day 390 for subjects receiving 2 doses and until Day 670 for subjects receiving 3 doses). For corticosteroids, this will mean prednisone ≥ 5 mg/day (for adult subjects), or equivalent. Inhaled and topical steroids are allowed.
- Long-acting immune-modifying drugs administered at any time during the study period (eg, infliximab).
- A vaccine not foreseen by the study protocol administered during the period starting the day of the first vaccination and ending 6 weeks after the last vaccination*, with the exception of inactivated influenza vaccine which can be administered up to 14 days before or from 30 days after the last study vaccination.

* In case an emergency mass vaccination for an unforeseen public health threat (eg, a pandemic) is recommended and/or organized by public health authorities outside the routine immunization program, the time period described above can be reduced if, necessary for that vaccine, provided it is used according to the local governmental recommendations and that the Sponsor is notified accordingly.

- Immunoglobulins and/or any blood products administered during the study period.
- Drug and/or alcohol abuse.

The Medical Monitor should be contacted if there are any questions regarding concomitant or prior therapy.

6.9 Dose Modification

Dose modifications are not planned or allowed in this study.

6.10 Treatment After the End of the Study

During the study conclusion visit, the Investigator will ask each subject if they are interested in participating in a booster study/long-term study. If a subject is not interested in participating in the booster study/long-term study the reason for refusal will be documented, when available, in the subject's eCRF.

The Sponsor will not provide any additional care to subjects after they completed the study.

7.0 DISCONTINUATION OF STUDY TREATMENT AND SUBJECT DISCONTINUATION/WITHDRAWAL

7.1 Discontinuation of Study Vaccine

A “withdrawal” from the study vaccine(s) refers to any subject who does not receive the complete treatment, ie, when no further planned dose is administered from the date of withdrawal. A subject withdrawn from the study vaccine(s) may continue further study procedures (safety or immunogenicity) if planned in the study protocol, as deemed appropriate by the Investigator.

Primary reason relative to premature discontinuation of the study vaccine(s) will be documented on the Vaccine Administration screen of the eCRF. The Investigator will document whether the decision to discontinue further vaccination was made by the subject himself/herself or by the Investigator, as well as which of the following possible reasons was responsible for withdrawal:

- AEs requiring expedited reporting.
- Nonserious AE (specify).
- Unsolicited nonserious AE.
- Solicited AE.
- Not willing to be vaccinated.
- Other (specify).

7.2 Subject Discontinuation/Withdrawal From the Study

- A subject may withdraw from the study at any time at his/her own request or may be withdrawn at any time at the discretion of the Investigator for safety, behavioral, compliance, or administrative reasons.
- If the subject withdraws consent for disclosure of future information, the Sponsor may retain and continue to use any data collected before such a withdrawal of consent.
- If a subject withdraws from the study, he/she may request destruction of any samples taken and not tested, and the Investigator must document this in the study center study records.
- See Section 1.3 for data to be collected at the time of study discontinuation and follow-up and for any further evaluations that need to be completed. Should a subject request or decide to withdraw from the study, all efforts must be made to complete and report the observations as thoroughly as possible up to the date of withdrawal. Subjects withdrawing due to an AE should be followed up according to the Follow-up Visit.
- Subjects withdrawn due to an AE will not be replaced.

From an analysis perspective, a “withdrawal” from the study refers to any subject who did not come back for the concluding visit foreseen in the protocol.

All data and samples collected until the date of withdrawal/last contact of the subject will be used for the analysis.

A subject is considered a “withdrawal” from the study when no study procedure has occurred, no follow-up has been performed and no further information has been collected for this subject from the date of withdrawal/last contact.

Investigators will make an attempt to contact those subjects who do not return for scheduled visits or follow-up.

The primary reason for study withdrawal will be documented in the eCRF. The Investigator will document whether the decision to withdraw a subject from the study was made by the subject himself/herself or by the Investigator, as well as which of the following possible reasons was responsible for withdrawal:

- AEs requiring expedited reporting.
- Unsolicited nonserious AE.
- Solicited AE.
- Protocol deviation.
- Withdrawal by subject, not due to an AE.*
- Migrated/moved from the study area.
- Lost to follow-up.
- Sponsor study termination.
- Other (specify).

*In case a subject is withdrawn from the study because he/she has withdrawn consent, the Investigator will document the reason for withdrawal of consent, if specified by the subject, in the eCRF.

Subjects who are withdrawn from the study because of SAEs/AEs must be clearly distinguished from subjects who are withdrawn for other reasons. Investigators will follow subjects who are withdrawn from the study as result of an SAE/AE until resolution of the event (see Section 8.3.3).

7.3 Lost to Follow-up

A subject will be considered lost to follow-up if he or she repeatedly fails to return for scheduled visits and is unable to be contacted by the study center.

The following actions must be taken if a subject fails to return to the study center for a required study visit:

- The study center must attempt to contact the subject and reschedule the missed visit as soon as possible and counsel the subject on the importance of maintaining the assigned visit

schedule and ascertain whether or not the subject wishes to and/or should continue in the study.

- Before a subject is deemed lost to follow-up, the Investigator or designee must make every effort to regain contact with the subject (where possible, 3 telephone calls and, if necessary, a certified letter to the subject's last known mailing address or local equivalent methods). These contact attempts should be documented in the subject's medical record.
- Should the subject continue to be unreachable, he/she will be considered to have withdrawn from the study.

8.0 STUDY ASSESSMENTS AND PROCEDURES

Study procedures and their timing are summarized in Section 1.3.

Protocol waivers or exemptions are not allowed unless necessary for the management of immediate safety concerns.

Immediate safety concerns should be discussed with the Sponsor immediately upon occurrence or awareness to determine if the subject(s) should discontinue study treatment.

Adherence to the study design requirements, including those specified in Section 1.3, is essential and required for study conduct.

All screening evaluations must be completed and reviewed to confirm that potential subjects meet all eligibility criteria. The Investigator will maintain a screening log to record details of all subjects screened and to confirm eligibility or record reasons for screening failure, as applicable.

Procedures conducted as part of the subject's routine clinical management (eg, blood count) and obtained before signing of ICF may be utilized for screening or baseline purposes provided the procedure met the protocol-specified criteria and was performed within the timeframe defined in Section 1.3.

Supplementary study conduct information not mandated to be present in this protocol is provided in the accompanying SPM. The SPM provides the Investigator and the study center personnel with administrative and detailed technical information that does not impact the safety of the subjects.

The maximum amount of blood collected from each subject over the duration of the study, will not exceed 200 mL. Repeat or unscheduled samples may be taken for safety reasons or for technical issues with the samples (refer to Section 8.2.3 for blood sampling related to safety and to Section 8.8.1 for blood sampling related to immunogenicity assessment).

During special circumstances (eg, COVID-19 pandemic), the specific guidance from local public health and other competent authorities regarding the protection of individuals' welfare must be applied. For the duration of such special circumstances, certain study procedures may be implemented for enrolled subjects (refer to Section 8.11 for further details).

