1.3 Schedule of Activities

Table 6 Schedule of Activities (Refer to Section 8.11 for Study Procedures to be Considered During Special Circumstances)

Type of contact	Screening ^a	Visit 1	Visit 2	Visit 3	Visit 4	Visit 5	Visit 6	Visit 7	Screening for Dose 3, Step 4	Visit 8 for Step 4	Visit 9 for Step 4	Visit 10 for Step 4	Visit 11 for Step 4
Timepoints	Day -15	Day 1	Day 8	Day 31	Day 38	Day 61	Day 180	Day 390	Day 476	Day 491	Day 498	Day 521	Day 670
Informed consent	●												
Informed consent addendum									●				
Check inclusion/exclusion criteria	●	●							●				
Collect demographic data ^b	●												
Medical history ^c	●												
Physical examination	●	● ^e	○ ^d	● ^e	○ ^d	○ ^d	○ ^d	○ ^d	●	● ^e	○ ^d	○ ^d	○ ^d
Vital signs (systolic/diastolic blood pressure and heart rate)	●	● ^e	○	● ^e	○	○	○	○	●	● ^e	○	○	○
Urine pregnancy test ^f	●	● ^e		● ^e					●	● ^e			
Measure/record height and weight	●												
Check contraindications to subsequent vaccination ^g				● ^e						● ^e			
Body temperature		● ^e		● ^e						● ^e			
Study group and treatment number allocation		○ ^e											
Treatment number allocation for subsequent dose				○ ^e						○ ^e			

Table 6 Schedule of Activities (Refer to Section 8.11 for Study Procedures to be Considered During Special Circumstances)

Type of contact	Screening ^a	Visit 1	Visit 2	Visit 3	Visit 4	Visit 5	Visit 6	Visit 7	Screening for Dose 3, Step 4	Visit 8 for Step 4	Visit 9 for Step 4	Visit 10 for Step 4	Visit 11 for Step 4
Timepoints	Day -15	Day 1	Day 8	Day 31	Day 38	Day 61	Day 180	Day 390	Day 476	Day 491	Day 498	Day 521	Day 670
Recording of administered treatment number		●		●						●			
Vaccine administration		●		●						●			
Blood sampling for antibody determination (humoral immunogenicity) (approximately 20 mL) – TNA and ELISA		● ^e		● ^e		●	●	●		● ^e		●	●
Optional blood sample for PBMC isolation (approximately 40 mL)						● ^k							
Blood sampling for hematology and biochemical analysis (approximately 5.5 mL) ^{h, i}	●	● ^{e, j}	●	● ^e	●		●	●	●	● ^e	●		●
Urine analysis (quantitative or semi-quantitative analysis)	●								●				
Record any concomitant medications/vaccinations	●	● ^e	●	● ^e	●	●	●	●	●	● ^e	●	●	●
Record any intercurrent medical conditions	●	● ^e	●	● ^e	●	●	●	●	●	● ^e	●	●	●
Distribution of the subject card	○												
Distribution of paper diary cards		○		○						○			

Table 6 Schedule of Activities (Refer to Section 8.11 for Study Procedures to be Considered During Special Circumstances)

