Type of contact	Screening ^a	Visit 1	Visit 2	Visit 3	Visit 4	Visit 5	Visit 6	Visit 7	Screening for Dose 3, Step 4	Visit 8 for Step 4	Visit 9 for Step 4	Visit 10 for Step 4	Visit 11 for Step 4
Timepoints	Day -15	Day 1	Day 8	Day 31	Day 38	Day 61	Day 180	Day 390	Day 476	Day 491	Day 498	Day 521	Day 670
Return of paper diary cards			○	○	○	○					○	○	
Diary card transcription by Investigator			●	●	●	●					●	●	
Recording of solicited AE (Day 1 to Day 7)		●	●	●	●					●	●		
Recording of unsolicited AE (Day 1 to Day 30)		●	●	●	●	●				●	●	●	
Recording of SAEs (all, fatal, related to study vaccine)		●	●	●	●	●	●	●	●	●	●	●	●
Recording of SAEs related to study participation, or to a concurrent GSK medication/vaccine	●	●	●	●	●	●	●	●	●	●	●	●	●
Recording of AEs of specific interest (pIMDs)		●	●	●	●	●	●	●	●	●	●	●	●
Recording of pregnancies		●	●	●	●	●	●	●	●	●	●	●	●
Study conclusion for individual subjects								● ^b					● ^m

AE = adverse event; D = Day; ELISA = enzyme-linked immunosorbent assay; eCRF = electronic case report form; GSK = GlaxoSmithKline Biologicals SA; iSRC = internal safety review committee; PBMC = peripheral blood mononuclear cell; pIMD = potential immune-mediated disease; SAE = serious adverse event; TNA = toxin neutralization assay.

Note: The double-line border following Day 61 indicates the analyses which will be performed on all data (ie, data that are as clean as possible) obtained up to Day 61.

- Used to indicate a study procedure that requires documentation in the individual eCRF.

- Used to indicate a study procedure that does not require documentation in the individual eCRF.
- ^a If the Investigator believes there is a reasonable justification to do so, screening procedures may be repeated (maximum 1 rescreening per subject is allowed). Only laboratory results from the Rescreening Visit, if it occurs, will be taken into consideration and recorded in the eCRF. Medical history, physical examination and review of inclusion/exclusion criteria must be repeated if a Rescreening Visit occurs. The subject can only be randomized once the Investigator receives the results and confirms the eligibility criteria.
- ^b Date of birth, sex, and race to be recorded in the subject's eCRF.
- ^c Medical occurrences that begin before the start of study treatment but after obtaining informed consent will be recorded in the subject's eCRF.
- ^d Physical examination, if deemed necessary by the Investigator or delegate.
- ^e To be performed prior to vaccination.

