3.0 OBJECTIVES AND ENDPOINTS

Table 9 Study Objectives and Endpoints

Objectives	Endpoints

Primary
 
 To evaluate the safety and reactogenicity profile of the C. difficile F2 fusion protein when administered with or without AS01B adjuvant as IM doses according to a 0, 1-month schedule, in healthy adults aged between 18-45 years and between 50-70 years followed by an additional dose administered approximately 15 months after Dose 2 in a subcohort of subjects aged 50-70 years, during the entire study period. 	
 Solicited local and general symptoms. 
 Occurrence of solicited local symptoms (any and Grade 3) within 7 days (Day 1 to Day 7) after each vaccination, in all subjects and in all groups. Occurrence of solicited general symptoms (any, Grade 3, related, and Grade 3 related) within 7 days (Day 1 to Day 7) after each vaccination, in all subjects and in all groups. Unsolicited AEs. 
 Occurrence of unsolicited AEs (any, Grade 3, related, Grade 3 related, and those resulting in a medically attended visit) within 30 days (Day 1 to Day 30) after each vaccination, according to the MedDRA classification, in all subjects and in all groups. SAEs. 
 Occurrence of SAEs from Dose 1 (Day 1) up to study end, in all subjects and in all groups. AEs of specific interest. 
 Occurrence of AEs of specific interest (pIMDs) from Dose 1 up to study end, in all subjects and in all groups. Laboratory parameters 
 Occurrence of hematological (white blood cells, platelets count, and hemoglobin level) and biochemical (alanine aminotransferase, aspartate aminotransferase, creatinine, and uric acid) laboratory abnormalities at Screening, Days 8, 31, 38, 180, 390, 476, 491, 498, and 670 and urinary laboratory abnormalities (protein, glucose, and blood) at Screening. (Grades will be based on the local laboratory normal ranges and derived from the FDA Toxicity Grading Scale for laboratory abnormalities).

Table 9 Study Objectives and Endpoints

Objectives	Endpoints
Secondary	

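### Section 8.0 limits blood to 200 mL per subject, but Table 6 schedules about 215 mL for a Dose 3 subject, or 255 mL with the optional PBMC sample

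*Protocol*

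**What the plan says.** Section 8.0 of the protocol sets a limit per person: "The maximum amount of blood collected from each subject over the duration of the study, will not exceed 200 mL". It then allows repeat or unscheduled samples for safety or technical reasons. The same section says of the schedule: "Adherence to the study design requirements, including those specified in Section 1.3, is essential and required for study conduct". It also refers to the Study Procedures Manual (SPM): "Supplementary study conduct information not mandated to be present in this protocol is provided in the accompanying SPM".

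Table 6 in Section 1.3 gives the volumes in three row labels:

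- "Blood sampling for antibody determination (humoral immunogenicity) (approximately 20 mL" per draw
- "Blood sampling for hematology and biochemical analysis (approximately 5.5 mL" per draw
- "Optional blood sample for PBMC isolation (approximately 40 mL", at Visit 5 in Step 4 only

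Subjects who receive two doses finish at Visit 7 (Day 390). Those who receive three finish at Visit 11 (Day 670), so for them the duration of the study includes every Dose 3 visit.

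**The concern.** For a Dose 3 subject who attends every visit, the stated volumes add up to more than the stated maximum. Section 8.0 requires both the schedule and the limit, and the protocol does not say which gives way.

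Either course has a cost. If all draws are taken, the trial exceeds a maximum that the protocol sets for each subject and that the consent documents may repeat. If the limit is observed, samples are lost or shortened late in follow-up, where the Dose 3 data lie. Table 9 lists the primary laboratory endpoint as "laboratory abnormalities at Screening, Days 8, 31, 38, 180, 390, 476, 491, 498, and 670", so Days 491, 498 and 670 are affected. Days 491, 521 and 670 are secondary-endpoint serology timepoints, and Day 521 is the cut-off for the second interim analysis.

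**Working it through.** **Inputs, from Table 6.**

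- Serology, about 20 mL each: Visits 1, 3, 5, 6, 7, 8, 10 and 11, so 8 draws, 5 of them by Visit 7. Table 9 (secondary endpoint) and Table 21 give the same timepoints.
- Safety blood, about 5.5 mL each: Screening, Visits 2, 3, 4, 6 and 7, Dose 3 screening, and Visits 8, 9 and 11, so 10 scheduled draws, 6 of them by Visit 7. Table 9 (primary endpoint) and the hematology timepoints in Table 25 agree. The Visit 1 safety draw is an optional retest and is left out of the base count.
- Optional PBMC sample: about 40 mL at Visit 5.

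**Totals** = 20 × serology draws + 5.5 × safety draws (+ 40 for PBMC, + 5.5 for the Visit 1 retest).

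| Schedule | Base | With PBMC | With PBMC and retest |
|---|---|---|---|
| Two doses | 5 × 20 + 6 × 5.5 = 133 | 173 | 178.5 |
| Three doses | 8 × 20 + 10 × 5.5 = 215 | 255 | 260.5 |

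The 200 mL figure therefore holds for the two-dose schedule and fails for the three-dose schedule. The Dose 3 visits add 3 × 20 + 4 × 5.5 = 82 mL.

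**Running total for a Dose 3 subject (mL).**

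| Day | Volume at visit | Without PBMC | With PBMC |
|---|---|---|---|
| 390 | 25.5 | 133 | 173 |
| 476 | 5.5 | 138.5 | 178.5 |
| 491 | 25.5 | 164 | **204** |
| 498 | 5.5 | 169.5 | 209.5 |
| 521 | 20 | 189.5 | 229.5 |
| 670 | 25.5 | **215** | 255 |

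**Where the limit is passed.**

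- Without PBMC, 200 − 189.5 = 10.5 mL remains for the 25.5 mL due at Day 670, a shortfall of 15 mL (15/200 = 7.5%).
- With PBMC, 200 − 178.5 = 21.5 mL remains for the 25.5 mL due at Day 491. Table 6 marks the Day 491 draws "To be performed prior to vaccination", so a PBMC donor reaches the limit before Dose 3 is given. The excess is 4 + 5.5 + 20 + 25.5 = 55 mL (55/200 = 27.5%).
- With PBMC and the Visit 1 retest, the excess is 60.5 mL (about 30%).

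**How far below nominal the draws would have to run.**

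- Averaged over all draws: 1 − 200/215 = 7.0% without PBMC; 1 − 200/255 = 21.6% with it.
- Over the draws after Day 390 only, assuming earlier draws were at nominal volume: 15/82 = 18.3% without PBMC; 55/82 = 67.1% with it.

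The second pair is the more relevant for a correction. Dose 3 subjects must have completed Visit 7, so their earlier draws are already taken when Dose 3 screening begins.

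**The case against.** The sum is not in dispute, and nothing in the protocol raises the limit or exempts the scheduled Dose 3 draws. The case on the other side concerns weight.

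- **The volumes are approximate and the base excess is small.** This stands. A non-donor conflicts only at Day 670. Section 8.8.2 ranks the neutralizing assays first when a sample is short, and SAP Section 3.3 drops ELISA, so a reduced Day 670 serology sample may lose nothing that the SAP analyses.
- **The larger excess depends on an optional sample.** This also stands. PBMC blood is taken only from consenting Step 4 subjects, and uptake is not stated.
- **Endpoint loss is conditional.** Nothing tells the site to stop drawing at 200 mL. If all draws are taken, the problem is one of protocol and consent consistency, with no effect on the analysis. At Day 491 a donor's 21.5 mL of room covers either sample in full, though not both.
- **Dropping ELISA is not settled in the protocol.** SAP version 3.0 (27 September 2021) removes it, but the later protocol Amendment 04 (2 December 2021) still lists it in Tables 6, 9 and 20. Per-assay volumes are not given, so whether smaller samples would suffice cannot be checked.
- **The SPM might settle precedence.** It was not available for review. Section 8.0 limits it to administrative and technical detail without impact on subject safety, so a per-subject blood limit belongs in the protocol.

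These points limit the consequence. They do not remove the contradiction.

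**Conclusion.** The concern holds. At the stated volumes, a Dose 3 subject who completes every scheduled draw gives 215 mL against a stated maximum of 200 mL, and a PBMC donor gives 255 mL. The 15 mL excess is minor and could be absorbed by slightly smaller draws. The 55 mL excess is not explained by rounding: it would need draws after Day 390 to average about two-thirds below nominal if the earlier ones were at nominal volume.

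The limit suits the two-dose schedule, which suggests that it was not revisited when the Dose 3 visits were added. The result rests on nominal volumes and full attendance; a subject with missed draws may stay under the limit, while rescreening or retests would add to the total. Table 21 plans about 60 subjects at Visit 8 and about 50 at Visit 11. No effect on any estimate is shown. The main issue is a stated maximum that the required schedule does not meet, with loss of Dose 3 samples as a conditional risk. It should be fixed.

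**What to change.** Reconcile Section 8.0 with Table 6 for Dose 3 subjects, with and without the PBMC sample, so that the maximum and the scheduled volumes agree. Either restate the maximum, or document reduced later volumes that the assays can support. The second route also requires the protocol and SAP to agree on whether ELISA is performed. State in the protocol which instruction takes precedence if the two conflict. Check that the Dose 3 consent addendum, which was not available for review, gives the same figure.

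The cost is a short protocol correction with the IRB/IEC handling described in Appendix 3, and possibly reconsent if the addendum states 200 mL. The analysis is unchanged if all draws are taken.
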